11.5 Review and reporting of serious adverse events

- 1) The investigator will report any serious adverse events to the sponsor within 24 hours of getting to know the occurrence of the event. The investigator will report detailed information to the sponsor by using the "Report of Serious Adverse Events" form within 2 days of getting to know the occurrence of the event (the date the event was known is regarded as day 0). The study site's own form may be used instead of the "Report of Serious Adverse Events". For additional reporting, new serious information (e.g., change in the name of the adverse event, causal relationship, outcome information, the severity category, etc.) should be reported to the sponsor according to the above rules when it becomes known.
- 2) The investigator will report the event to the study site according to the study site's operating procedures.
- 3) The investigator will provide any additional information (e.g., autopsy reports, late-stage medical records, and other necessary information) on reported serious adverse events, as requested by the sponsor.

11.6 Reporting of adverse events of special interests (AESIs)

The investigator should report to the sponsor promptly when an AESI is noted. For atopic dermatitis and skin symptoms with edematous erythema or scaling, the necessary information (details of the symptoms/signs and the basis for determining the causal relationship with the IP) should be stated in the CRF. Any additional information should be provided, as requested by the sponsor.

At the time of physical examination on the day of follow-up visit, the final outcome of any AESI "not recovered/not resolved" falling under 1) below should be obtained according to 2). Concomitant medications and therapies will also be collected according to Sections [9.3.2.1](#) and [9.3.2.2](#).

- 1) AESIs to be obtained
 - a) AEs requiring discontinuation of study treatment
 - b) Asthma
 - c) Atopic dermatitis
 - d) Skin symptoms with edematous erythema or scales
- 2) Period to obtain AESIs

AESIs should be collected until the earlier of the following dates to obtain the final outcome information (the outcome and the date of outcome/outcome obtained).

 - Date of recovering or recovered
 - Date 6 months after the last dose of IP

11.7 Photography

Among AESIs, "atopic dermatitis" and "skin symptoms with edematous erythema or scales" will be photographed to examine the detailed skin findings of the events. Other adverse events of which the principal investigator or subinvestigator considers it necessary to take photographs will also be photographed.

The photographs taken will be used as a record of the occurrence of adverse event and a reference for safety evaluation.

11.8 Reporting of the Pregnancy of the Participant

- 1) If obtaining the information on the pregnancy of the participant who received the IP, the investigator or subinvestigator must immediately discontinue study treatment and take appropriate action for the participant, and follow up the participant until the completion of the pregnancy (e.g., delivery).
- 2) The investigator or subinvestigator will also report detailed information to the sponsor by using the "Report for Pregnancies during the Study" form.
- 3) Participant pregnancies are not regarded as adverse events.

11.9 Rationale for Safety Endpoints

- 1) In terms of safety protection of participants, it is considered decided that the echocardiography should be carried out periodically. Echocardiography is a useful examination for screening of pulmonary arterial hypertension caused by SSc, and the Guidelines for Diagnostic Criteria, Severity Classification and Clinical Practice of Systemic Sclerosis recommends performing echocardiography. Pulmonary arterial hypertension caused by SSc has a poor prognosis and requires early detection

11.10 Follow-up of Adverse Events

For all adverse events developing during the study period (from the time of informed consent to the day of follow-up visit), the investigator or subinvestigator will provide appropriate treatments, and follow up until the event recovers to normal condition (within the reference ranges for laboratory test values), to the level before the consent was obtained, or until the investigator or subinvestigator considers that medical follow-up is no longer required. However, AESIs defined in Section 11.6 1) should be obtained according to Section 11.6 even if the investigator or subinvestigator considers that their follow-up is not medically necessary.

11.11 Malfunctions of DCS

11.11.1 Reporting of Malfunctions of DCS

In the event of a malfunction of DCS, the principal investigator or subinvestigator will promptly report it to the sponsor according to the "Procedures for the Management of Investigational Products."

11.11.2 Collection and Reporting of Malfunction Information on DCS occurring at the Stage of Use on Participants

The principal investigator or subinvestigator will obtain the information shown in Table 11-2 on DCS malfunctions occurring after prescription to participants and record them in the CRFs

Table 11-2 Information to be obtained for DCS Malfunction Occurring after Prescription to Participants

Information	Details
Details of malfunction	Structural, material, functional defects, etc.
Presence or absence of SAEs (including possibility)	Presence or absence of SAEs or possibility of occurring SAEs due to malfunction
Date of incident	Date of incident
Presence or absence of AEs associated with the malfunction of DCS	Presence or absence of adverse events occurring associated with the malfunction of DCS

If a SAE occurs or may occur associated with a DCS malfunction, the SAE information together with the detailed information of the SAE will be sent to the sponsor in a "Serious Adverse Event and Malfunction Report" form to according to the procedures described in "11.5 Collection and Reporting of Serious Adverse Events." The "Serious Adverse Event and Malfunction Report" may be used in the form of the medical institution.

11.11.3 Storage of Malfunctioning DCS

The IP manager shall store malfunctioning DCSs appropriately at the study site, not discarding them.

11.12 Anticipated Adverse Drug Reactions

See the investigator's brochure of nemolizumab for anticipated adverse drug reactions of nemolizumab.

12. Biomarkers

12.1 Measurements of Biomarkers

- 1) Variable to be measured
 - a) IL-31
 - b) KL-6, SP-D, NT-proBNP
 - c) Exploratory biomarkers
- 2) Collection of blood samples
 - a) Blood samples will be collected on the day of study treatment initiation, at Week 4, 8, 12, 16, 20, 24, and 36, and Week 52 or on the day of visit for discontinuation. On the days of study treatment, blood samples will be collected before administration of IP.
 - b) Blood samples will be collected on the day of study treatment initiation, at Week 4, 12, 24, and 36, and Week 52 or the day of visit for discontinuation. On the days of study treatment, blood samples will be collected before administration of IP.
 - c) Blood samples will be collected on the day of study treatment initiation, at Week 12, 24, and Week 52 or the day of visit for discontinuation. On the days of study treatment, blood samples will be collected before administration of IP.

The collected blood samples will be centrifuged to separate the serum, and the serum samples will be stored frozen until measured. The amount of blood collected, centrifugal conditions, and storage conditions are specified in a separate operating procedure.

12.3 Measurement Method and Reporting of Results

1) Measurement methods

- IL-31 and exploratory biomarkers will be measured using the Enzyme-Linked Immuno Sorbent Assay (ELISA) method. The measurements will be performed by [REDACTED] Corporation according to its assay protocol.
- KL-6, SP-D and NT-proBNP will be measured by [REDACTED] Corporation according to its assay protocol.
- Exploratory biomarkers will be measured using the Electro Chemi-Luminescence (ECL) method. The measurements will be performed by [REDACTED] Corporation according to its assay protocol.

2) Report of measurement results

- IL-31, KL-6, SP-D, NT-proBNP and exploratory biomarkers
[REDACTED] Corporation will prepare and submit a report of analysis results to the sponsor.

13. Pharmacokinetics

13.1 Pharmacokinetic Measurements

1) Variable to be measured

Serum concentration of nemolizumab

2) Collection of blood samples

Blood samples will be collected on the day of study treatment initiation, at Week 1, 2, 4, 8, 12, 16, 20, 24, and 36, Week 52 or on the day of visit for discontinuation, and on the day of follow up. On the days of study treatment, blood samples will be collected before administration of IP.

The collected blood samples will be centrifuged to separate the serum, and the serum samples will be stored frozen until measured. The amount of blood collected, centrifugal conditions, and storage conditions are specified in a separate operating procedure.

13.2 Pharmacokinetic Outcome Measures

- Serum concentration of nemolizumab
- Pharmacokinetic parameters: C_{max} , t_{max} , $AUC_{0-28day}$, AUC_{last}

- Rationale for selection

Parameters necessary and evaluable to examine pharmacokinetics of nemolizumab have been selected in reference to “Clinical pharmacokinetic studies on drugs (PFSB/ELD No.796 of June 1, 2001).”

13.3 Measurement Method and Reporting of Results

1) Measurement method

Serum concentration of nemolizumab will be measured using the ELISA method. The measurements will be performed by [REDACTED] Laboratories, Ltd. according to its assay protocol.

2) Report of measurement results

██████████ Laboratories, Ltd. will prepare and submit a report of analysis results to the sponsor.

14. Immunogenicity

14.1 Immunogenicity Measurements

1) Variable be measured

Serum anti-nemolizumab antibody

2) Collection of blood samples

Blood samples will be collected on the day of study treatment initiation, at Week 24 and 36, Week 52 or on the day of visit for discontinuation, and on the day of follow up. On the days of study treatment, blood samples will be collected before administration of IP.

The collected blood samples will be centrifuged to separate the serum, and the serum samples will be stored frozen until measured. The amount of blood collected, centrifugal conditions, and storage conditions are specified in a separate operating procedure.

14.2 Immunogenicity Outcome Measures

1) Serum anti-nemolizumab antibody

2) Neutralizing antibody concentrations

- Rationale for selection

The variables have been selected to evaluate the effects of the development of anti-nemolizumab antibodies to efficacy and safety in participants.

14.3 Measurement Method and Reporting of Results

1) Measurement method

The serum anti-nemolizumab antibody will be measured using the ECL method. When anti-nemolizumab antibodies are detected, their characteristics will be determined using the cell-based assay (CBA) method. The measurement will be performed by ██████████ Corporation according to its assay protocol.

2) Report of measurement results

██████████ Corporation will prepare and submit a report of analysis results to the sponsor.

15. Comprehensive Measurement of Autoantibodies

Comprehensive measurement of autoantibodies will be performed to determine the disease state of SSc and explore the patient-group for whom nemolizumab is effective.

15.1 Measurement Method and Reporting of Results

1) Collection of blood samples

Blood samples will be collected on the day of study treatment initiation, at Week 24, and Week 52 or on the day of visit for discontinuation. On the days of study treatment, blood samples will be collected before administration of IP.

The collected blood samples will be centrifuged to separate the serum, and the serum samples will be stored frozen until measured. The amount of blood collected, centrifugal conditions, and storage

conditions are specified in a separate operating procedure.

2) Measurement method

Autoantibodies will be measured comprehensively using HuPEX™ protein array. The measurement will be performed by [REDACTED] Corporation according to its assay protocol.

3) Report of measurement results

[REDACTED] Corporation will prepare and submit a report of analysis results to the sponsor. Measurement results will not be included in the clinical study report and will be summarized in a separate report.

16. CyTOF measurement

CyTOF measurement will be performed to explore the mechanism of action of nemolizumab in SSc.

16.1 Measurement Method and Reporting of Results

1) Collection of blood samples

Blood samples will be collected on the day of study treatment initiation, at Week 24, and Week 52 or on the day of visit for discontinuation. On the days of study treatment, blood samples will be collected before administration of IP.

PBMC preparation of collected blood samples will be performed by the day following sample collection. The amount of blood to be collected and storage conditions are specified in a separate operating procedure.

2) Measurement method

Measurement will be performed by [REDACTED], Inc. according to its assay protocol.

3) Report of measurement results

[REDACTED], Inc. will prepare and submit a report of analysis results to the sponsor. Measurement results will not be included in the clinical study report and will be summarized in a separate report.

17. Statistical Analysis

The major plans for statistical analyses are presented below. The details are provided in the Statistical Analysis Plan. This plan will be fixed prior to database lock on through discussions on data review etc.

17.1 Analysis Sets

17.1.1 Efficacy Analysis Set (Full Analysis Set: FAS)

The efficacy analysis set includes all participants assigned to treatment except for those who meet any of the following criteria:

- 1) Participants who are found not to have SSc
- 2) Participants who have received no dose of nemolizumab at all after assigned to treatment
- 3) Participants with no efficacy data at all after assigned to treatment

17.1.2 Safety Analysis Set

The safety analysis set includes all participants assigned to treatment except for those who meet any of the following criteria:

- a) Participants who have received no dose of nemolizumab at all after assigned to treatment
- 2) Participants with no safety data at all after assigned to treatment

17.1.3 Pharmacokinetics Analysis Set

The pharmacokinetics analysis set includes all participants assigned to treatment except for those who meet any of the following criteria:

- 1) Participants who have received no dose of nemolizumab at all after assigned to treatment
- 2) Participants with no pharmacokinetic data at all after assigned to treatment

17.1.4 Biomarker Analysis Set

The biomarker analysis set includes all participants assigned to treatment except for those who meet any of the following criteria:

- 1) Participants who have received no dose of nemolizumab at all after assigned to treatment
- 2) Participants with no biomarker data at all after assigned to treatment

17.2 Data Handling

17.2.1 Common Rules

- a) Handling of missing values
The missing values will not be imputed.
- 2) Handling of data on the day of visit for discontinuation
The data measured or evaluated on the day of visit for discontinuation will be handled as the data of the relevant evaluation period if the visit is within the allowance of any visit for evaluation period. However, such data will not be included in the analysis if another data has been obtained in the relevant evaluation period.

17.2.2 Data Handling on Pharmacokinetics

- 1) Handling of values below the lower limit of quantification (BLQ) and missing values for serum drug concentration data
Values BLQ will be handled as follows and missing values will not be imputed.
 - a) Tabulation: They will be reported as BLQ.
 - b) Changes over time and profiles and summary statistics: They will be replaced by 0. However, if the number of participants with BLQ values exceeds half number of participants in pharmacokinetic analysis set, the summary statistics of serum drug concentrations at that time point will not be calculated and reported as N.C. (not calculated).
- 2) Handling of pharmacokinetic parameters not calculable
Parameters not calculable should be handled as follows:
 - a) Tabulation: They will be reported as N.C.
 - b) Summary statistic: They will be left missing. However, if the number of unevaluable participants for a pharmacokinetic parameter exceeds half of participants to be evaluated, the summary statistic of the parameter will not be calculated and reported as N.C.

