17.3.4 Analyses of Drug Concentrations and Pharmacokinetic Parameters

The following variables will be summarized on the pharmacokinetic analysis set.

1) Serum concentrations of nemolizumab

- a) Summary statistics including coefficient of variation and geometric mean of serum nemolizumab concentrations will be calculated by time point.
 - b) The serum nemolizumab concentration-time profile will be created using mean serum drug concentrations and their standard deviations.
 - c) The serum nemolizumab concentration-time profile will be created by participant.
 - d) The serum nemolizumab concentration-time profile will be created by participant where participants who tested positive for the first time after study treatment (in blue), those who had tested positive since before treatment (in red), and those who tested negative at all time points (in black) for anti-nemolizumab antibodies in serum in the confirmatory test will be identified by color.
- 2) Pharmacokinetic parameters (C_{max} , t_{max} , $AUC_{0-28Day}$, and AUC_{last})
- Summary statistics including coefficient of variation and geometric mean of parameters will be calculated.

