17.4 Determination of Sample Size

17.4.1 Target Sample Size

The target sample size for this study is 8 participants.

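### Setting BLQ concentrations to 0 conflicts with the required geometric mean: with 1 to 4 of 8 participants BLQ it is 0 or not computable, and the CV reflects the substituted zeros

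*Combined protocol and SAP*

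**What the plan says.** Section 17.2.2 1) of the protocol sets the rule for serum concentrations. Individual BLQ values are listed as BLQ. For everything else: "Changes over time and profiles and summary statistics: They will be replaced by 0". One safeguard follows: "if the number of participants with BLQ values exceeds half number of participants in pharmacokinetic analysis set", the statistics for that time point are given as N.C. Missing concentrations are left missing: "Values BLQ will be handled as follows and missing values will not be imputed".

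Section 17.3.4 1) a) then asks for statistics that include the geometric mean: "Summary statistics including coefficient of variation and geometric mean of serum nemolizumab concentrations will be calculated by time point". Neither section excepts the geometric mean from the zero substitution.

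The pharmacokinetic analysis set (17.1.3) leaves out participants who were never dosed and the following: "Participants with no pharmacokinetic data at all after assigned to treatment". It does not require a sample at any particular visit. On size, 17.4.1 says: "The target sample size for this study is 8 participants".

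All three protocol versions in the combined document carry the same text on these points.

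**The concern.** A geometric mean needs strictly positive values. Under the two rules taken together, one BLQ participant fixes the geometric mean at 0, or leaves it undefined if it is computed from logs, whatever the others measured. The CV is still computable, but it then mainly describes how many zeros were put in.

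Pharmacokinetics belongs to the secondary objective (section 2.2), and in a descriptive study of 8 participants these tables carry much of that result. If the conflict is noticed only when the tables are run, someone must choose a convention after seeing which values are BLQ. There is also a smaller question of whether the suppression rule counts against the right number when some participants have no sample.

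**Working it through.** The plan gives no numerical result for this rule, so there is no figure to reproduce. The check applies the rule as written.

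**Inputs.** Set size 8 (17.4.1); substitution by 0 and suppression above half of the set (17.2.2); half-life 12.6 to 14.6 days in atopic dermatitis (8.3); follow-up sample 84 ± 7 days after the last dose (9.2.8, 9.3.7). The limit of quantification is not given.

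**1. When suppression applies.** With k BLQ values in a set of 8, N.C. requires k > 8/2 = 4, so k = 5 or more. For k = 1 to 4, statistics are produced.

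**2. Geometric mean.** GM = (x₁ × … × x₈)^(1/8) = exp(mean of log x). Any x = 0 makes the product 0, and log 0 is undefined. As an illustration, take 1.0, 1.3, 1.6, 2.0, 2.4, 3.0, 3.6 and 4.5, and set the lowest k to 0:

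| BLQ of 8 | N.C.? | Geometric mean | Arithmetic mean |
|---|---|---|---|
| 0 | no | 2.17 | 2.43 |
| 1 | no | 0 (undefined by logs) | 2.30 |
| 4 | no | 0 (undefined by logs) | 1.69 |
| 5 or more | yes | – | – |

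The zeros in the third column do not depend on the values chosen.

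**3. CV (taken as SD/mean, divisor n − 1).** Suppose all measurable values equal c, so their own CV is 0%.
- One zero in eight: mean 0.875c, SD = c√(0.875/7) = 0.354c, CV = 40%.
- Four zeros in eight: mean 0.5c, SD = c√(2/7) = 0.535c, CV = 107%.

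**4. Which visit.**
- Follow-up, day 84: 84/14.6 = 5.8 and 84/12.6 = 6.7 half-lives, leaving 1.9% and 1.0% of one dose's level. Over the ± 7 day window the range is 2.6% (77/14.6) to 0.7% (91/12.6).
- Four-weekly pre-dose samples and Week 52, 28 days after a dose: 28/14.6 = 1.9 and 28/12.6 = 2.2 half-lives, leaving about 26% and 21%.
- Day 1 pre-dose: participants have never received nemolizumab (exclusion 16), so all samples are expected to be BLQ. With all 8 sampled, N.C. applies.

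**5. Denominator.** Let m of 8 participants have a sample. The rule as written still needs k > 4; counting sampled participants would need k > m/2.

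| Sampled (m) | Largest BLQ share not suppressed | k at which the two rules differ |
|---|---|---|
| 8 | 4/8 = 50% | none |
| 7 | 4/7 = 57% | 4 |
| 6 | 4/6 = 67% | 4 |
| 5 | 4/5 = 80% | 3, 4 |
| 4 | 4/4 = 100% | 3, 4 |

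With 4 BLQ of 5 sampled, statistics would be reported from four zeros and one value. Their CV is √0.2/0.2 = 224%, whatever that value is.

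**The case against.** The case for leaving this alone has several parts.

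- **Reach.** A reader might infer that every time point with a BLQ value is affected. That is not so: at 5 or more BLQ of 8 the plan already gives N.C. On the stated half-life only the follow-up visit comes plausibly close. Even there, 1.0% to 1.9% is the remainder of one dose. Accumulation from four-weekly dosing multiplies it by about 1/(1 − 0.214) = 1.27 to 1/(1 − 0.265) = 1.36, giving roughly 1.3% to 2.5%. Without the quantification limit, nobody can say that values will be BLQ. This stands.
- **Harm.** A reader might infer that conclusions on washout or anti-drug antibodies would be distorted. The documents do not support that. BLQ values are listed as such, the median, quartiles and range are planned (17.3), and 17.3.4 provides individual profiles coloured by antibody status. Parameters that cannot be calculated have their own rule in 17.2.2 2). A printed 0 would also be conspicuous. This stands.
- **Denominator.** A reader might call the analysis set the wrong denominator. It is explicit and reproducible, and the choice matters only when samples are missing. All dosed participants are scheduled for follow-up (section 3), and no dropout rate is given. What remains is an inconsistency: 17.3.3 uses participants observed at the time point, and 17.2.2 2) b) uses those to be evaluated.
- **Deferral.** Section 17 leaves details to a Statistical Analysis Plan fixed before database lock, and 17.5 provides for a review of data handling. A convention could be set there, but none appears in the documents supplied, and the two rules given do conflict.

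**Conclusion.** The point holds in limited form. As written, 17.2.2 1) b) and 17.3.4 1) a) cannot both yield a meaningful geometric mean when 1 to 4 of 8 participants are BLQ. The result is 0 or undefined, and the CV is driven by the substitution (40% from one zero and 107% from four, where the measured values do not vary at all). This is a contradiction between stated rules, not just missing detail.

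Its practical size rests on three assumptions: a pharmacokinetic set of 8, a half-life in systemic sclerosis like that quoted for atopic dermatitis, and a quantification limit within the range of the follow-up concentrations. Only descriptive pharmacokinetic summaries are touched; the mRSS endpoint is not. The denominator is a secondary matter of consistency and has no effect when everyone is sampled. The correction is worth making before the plan is fixed because it is cheap and avoids a choice made after seeing the BLQ pattern.

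**What to change.** In 17.2.2 1) b), or in the detailed analysis plan:

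1. Keep 0 for arithmetic summaries and profiles. Report the geometric mean as N.C. at any time point with at least one BLQ value, and print the number BLQ beside the median and range already planned. The count tells the reader when a CV or a minimum of 0 comes from substitution.
2. Base the more-than-half trigger on participants with a sample at that time point, in line with 17.3.3.

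Substituting half the quantification limit (LLOQ) for the geometric mean alone is not advised, because two substitutions would then describe one visit. With four BLQ values and four at 1.05 × LLOQ, the arithmetic mean with zeros is 4 × 1.05/8 = 0.525 LLOQ, while the geometric mean is √(0.5 × 1.05) = 0.725 LLOQ. A geometric mean above the arithmetic mean cannot occur on one set of values.

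The cost is two sentences and no new data. The downside is that visits with any BLQ value will show no geometric mean.
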